Sponsor [name], Oslo University Hospital

Phase and study type Phase IV, interventional.

Investigational Medical Product (IMP) (including active comparator and placebo) : Pentrox 3 ml@/N02B G09/Inhalation vapour, liquid
Fentanyl 0.025 mg/N01A H01/Concentrate and solvent for solution for injection
Fentanyl 0.05 mg/N01A H01/Concentrate and solvent for solution for injection
Placebo: NaCl 9 mg/ml (sodium chloride) Concentrate for solution for injection and inhalation

Centers: Oslo University Hospital, Oslo, Norway.

Study Period: Estimated date of first patient enrolled: 01.03.19

Anticipated recruitment period: 1 year and 10 months

Estimated date of last patient (volunteer) completed: 31.12.2020

End of study (last visit of volunteer): 31.12.2020

Treatment Duration: Expected treatment duration pr. Patient: 2 hours x 4 treatments = 8 hours

Follow-up: Expected follow-up period pr. Patient: Each treatment duration is 2 hours. No further follow-up visits.

Objectives The aim of this study is to determinate equipotent doses of inhaled metoxyflurane vs. intravenous fentanyl.

Endpoints: Primary endpoint: NRS (numeric rating scale, 0-10) scores during CPT 5 minutes after drug administration.

Secondary endpoint: NRS scores during CPT 20 minutes after drug administration.

Study Design: A randomized, double blind, placebo-controlled crossover study.

Main Inclusion Criteria: The volunteers should be in good health and not have any chronic illness

Main Exclusion Criteria No use of pain medication and complementary medicine the last 2 days before a session. Previous substance abuse, pregnancy and known allergies or serious side effects to opioids or metoxyflurane

Sample Size:	12 volunteers.
Efficacy Assessments:	Numeric rating scale (NRS) for pain, from 0 to 10. 0 = no pain to 10 = worst pain imaginable.
Safety Assessments:	Pulsoxymetry, end tidal CO ₂ and ECG will be continuously monitored during the study. Necessary acute medical equipment is available (Lærdalsbag, suction, intravenous liquid, naloxone. In addition anesthetic drugs: adrenalin, atropine and ephedrine). Respiration frequency and non-invasive blood pressure will be recorded every 5. min
Other Assessments:	Not applicable.

TABLE OF CONTENTS

CONTACT DETAILS	2
SIGNATURE PAGE.....	4
PROTOCOL SYNOPSIS.....	5
TABLE OF CONTENTS.....	7
LIST OF ABBREVIATIONS AND DEFINITIONS OF TERMS.....	10
1 INTRODUCTION	11
1.1 Background – Disease	11
1.2 Background - Therapeutic Information	11

1 INTRODUCTION

1.1 Background

Traumatized patients frequently experience pain prehospital due to the fear of adverse cardiovascular effects (e.g. hypotension) and respiration depression of opioid treatment, leading to insufficient analgesia.(1,2) Therefore, there is of interest to investigate other analgesics that do not have these adverse effects.

In Norway, methoxyflurane has been approved for the emergency relief of moderate to severe trauma pain in conscious adult patients. Methoxyflurane (Penthrox®) do not have these adverse effects (hypotension and respiration depression). It is easy to administrate via an inhalator, and is therefore suitable for use prehospital. This would possible help to treat pain better prehospital.

There exists no data of how effective methoxyflurane is as an analgesic compared to an opioid. The aim of this study is to determinate the equipotent doses of inhaled methoxyflurane vs. intravenous fentanyl.

1.2 Pre-Clinical & Clinical Experience with Investigational Medicinal Product (IMP)

Methoxyflurane (Penthrox® - inhalation vapour, liquid – C₃H₄Cl₂F₂O, ATC code: N02B G09) is a halogenated ether first used clinically as a volatile inhalational anesthetic when introduced in the 1960s.(3) Gradually the use of methoxyflurane as an anesthetic agent declined because of serious dose-related nephrotoxicity.(4) There have also been reports of hepatic failure or hepatitis. Therefore, methoxyflurane is contraindicated in patients with clinically renal impairment, and should be used with care in patients with hepatic dysfunction. There are no reports of renal toxicity in the literature at the current dose recommendation of 3 ml, repeated once with a maximum of 15 ml/week.(5-7) It has been calculated that an adult dose of 20-24 g methoxyflurane is associated with subclinical nephrotoxicity (6.0 ml delivers < 1.5 g).(8) Methoxyflurane also demonstrated an analgesic effect.(4) In the past 30 years methoxyflurane has been used as an analgesic in Australia and New Zealand. The drug has mostly been used in the emergency department and in a prehospital setting in conscious patients.(5) It is easy to administrate and has a fast onset of pain relief, approximately 5 min.(9,10)

One randomized, double-blind, placebo-controlled study of the efficacy and safety of methoxyflurane for the treatment of acute pain has been conducted.(11,12) Minor trauma patients were randomized in a 1:1 ratio to receive methoxyflurane (up to 6 ml) or placebo (normal saline), both via a Penthrox inhaler. Methoxyflurane was well tolerated. It was superior to placebo with respect to analgesic effect. No serious adverse effects were observed like e.g. hypotension or respiratory problems compared to placebo. The patients were not hypovolemic.

The opioid fentanyl (Fentanyl® - intravenous, liquid - C₂₂H₂₈N₂O. ACT: N01A H01) is used as standard therapeutic treatment for acute pain and acute operative pain. Fentanyl is a pure opioid receptor agonist with central and peripheral effects.

1.3 Rationale for the Study and Purpose

Traumatized patients frequently experience pain prehospital due to the fear of adverse cardiovascular effects (e.g. hypotension) and respiration depression of opioid treatment, leading to insufficient analgesia.(1,2) Therefore, there is of interest to investigate other analgesics that do not have these adverse effects.

In Norway, methoxyflurane has been approved for the emergency relief of moderate to severe trauma pain in conscious adult patients. Methoxyflurane (Penthrox®) do not have these adverse effects (hypotension and respiration depression). It is easy to administrate via an inhalator, and is therefore suitable for use prehospital. This would possible help to treat pain better prehospital.

There exists no data of how effective methoxyflurane is as an analgesic compared to an opioid. The aim of this study is to determinate the equipotent doses of inhaled methoxyflurane vs. intravenous fentanyl.

Twelve healthy volunteers (18 – 64 years) will be enrolled in a randomized, double blind, placebo-controlled, crossover study using a standard experimental pain model: CPT- Cold pressor test (ice water). Our group has used this experimental pain model in earlier studies and a crossover study is suitable to compare different drugs.(13,14)

Possible side effects will be recorded for both metoxyflurane and fentanyl: sedation, dizziness, itching, nausea and vomiting. Respiration frequency and non-invasive blood pressure will be recorded every as possible low blood pressure or respiration depression can occur.

The aim of this study is to determinate equipotent doses of inhaled metoxyflurane vs. intravenous fentanyl. We have chosen to compare with fentanyl (the comparator) because it is a well-known drug in clinical practice for acute pain treatment. In addition, both drugs have a fast onset (minutes) and the analgesic effect last for approximately the same time interval (20-30 min). Therefore, they are comparable in a clinical setting.

There exists no exact data of equipotent doses between metoxyflurane and fentanyl, only retrospective clinical data. One retrospective study compared intranasal fentanyl with inhaled metoxyflurane for visceral pain prehospital in 1024 patients.(10) The initial dose of fentanyl was 0.018 mg and the total mean dose at hospital arrival was 0.036 mg. In the metoxyflurane group 51.9% received 3 ml, a second dose was used in 41.9% and 6.2% received a third dose. Metoxyflurane produced the greatest initial pain scores reduction, and intranasal fentanyl provided greater pain reduction by hospital arrival.

From these data we have chosen two doses of fentanyl to be compared with 3 ml Pentrox: 0.025 mg and 0.05 mg intravenous. Both drugs will also be compared to placebo (NaCl 9 mg/ml).

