2 STUDY OBJECTIVES AND RELATED ENDPOINTS

The aim of this study is to determinate equipotent doses of inhaled metoxyflurane vs. intravenous fentanyl. We have chosen to compare with fentanyl because it is a well-known drug in clinical practice. In addition, both drugs have a fast onset (minutes) and the analgesic effect last for approximately the same time interval (20-30 min). Therefore, they are comparable in a clinical setting.

- 2.1 **Primary Endpoint** NRS (numeric rating scale) scores during CPT 5 minutes after drug administration.
- 2.2 **Secondary Endpoints** NRS scores during CPT 20 minutes after drug administration (15 min after last CPT).

The table below represent the study's timeline:

Time (min)	- 15	-10	-5	0	5	10	15
Control (C)	CPT		placebo (NaCl) i.v. placebo (NaCl) inhal; continuous	CPT			CPT
Fentanyl (F1)	CPT		F1 0.025 mg i.v. placebo (NaCl) inhal; continuous	CPT			CPT
Fentanyl (F2)	CPT		F2 0.05 mg i.v. placebo (NaCl) inhal; continuous	CPT			CPT
Metoxyflurane (M)	CPT		placebo (NaCl) i.v. M 3 ml inhal; continuous	CPT			CPT

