5.5 Schedule Modifications

No dose modifications are allowed.

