6 STUDY PROCEDURES

6.1 Flow Chart

Screening period within 1-14 days of treatment. Inclusion/exclusion evaluation. A medical history will be performed.

Three pilots will be performed before the study start to investigate whether the two selected doses are representative to compare with the 3 ml metoxyflurane dose. If the pilots demonstrate large differences in the CPT scores at time zero between the selected fentanyl doses and metoxyflurane, a change in the protocol has to be performed. This will lead to an application to REK about the changes (and the Norwegian Medicines Agency).

Flow chart:

Time (min)	-15	-10	-5	0	5	10	15
Control (C)	CPT		placebo (NaCl) i.v. placebo (NaCl) inhal; continuous	CPT			CPT
Fentanyl (F1)	CPT		F1 0.025 mg i.v. placebo (NaCl) inhal; continuous	CPT			CPT
Fentanyl (F2)	CPT		F2 0.05 mg i.v. placebo (NaCl) inhal; continuous	CPT			CPT
Metoxyflurane (M)	CPT		placebo (NaCl) i.v. M 3 ml inhal; continuous	CPT			CPT

Abbreviations: NaCl: natriumchloride, i.v: intravenously, inhal: inhalation, CPT: Cold pressor test.

Each session starts with a CPT (time -15 minutes). Then a 10 minutes rest before the subject receives a syringe of either NaCl or a dose of fentanyl intravenously (time -5 min). At the same time the subject begin to inhale either metoxyflurane or NaCl through the inhalator. The subject should first take 10 breath through the inhalator. This will take approximately 1-1.5 minutes. The subject then take a break, and then inhale the rest of the dosage before time zero.

At time zero a new CPT will be performed. At time 15 min the last CPT will be performed.

The subjects will undergo CPT (cold pressor test) to determine the analgesic effect of the drugs.(13,14) The CPT will be conducted using a temperature-controlled bath with circulating 3°C water (FP 45-HE Refrigerated/Heating Circulator,

Julabo Labortechnik, 77960 Seelback, Germany). The subjects submerge their right hand to the wrist with fingers abducted for up to 90 s. The endpoints are NRS scores every 10 s. This test will be performed 3 times for each session.

The actual implementation of the study will take 30 minutes. We estimate 30 minutes of preparation and 1 hour of observation after the execution of the protocol. Totally, each session will last for 2 hours.

A cannula will be placed on the subject left hand back. The right hand will be submerged into the ice water.

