10 STATISTICAL METHODS AND DATA ANALYSIS

10.1 Determination of Sample Size

The power analysis is based on data from one of our previous study using the same model, the cold pressor test.(13)

This is a crossover study. Data on standard deviation of differences between the conditions in a paired comparison is used in the calculation. nQuery Advisor software was used to calculate the sample size and to do the power analysis" A sample size of 10 will have 80% power to detect a difference in means of 0,500 (e.g. a First condition mean, of 6,000 and a Second condition mean of 5,500), assuming a standard deviation of differences of 0,500, using a paired t-test with a 0,050 two-sided significance level . We will include 12 subjects to achieve a more exact block-randomization.

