10.5 Statistical Analysis

10.5.1 Primary analysis and Secondary analysis

The linear mixed-model procedure will be used to compare the effect of different treatments in the NRS in the cold-pressor pain model. This is a variance component model that takes into account correlations/dependence as a result of repeated treatments, carryover effects, and repeated observations in each treatment session on each subject. This statistical analysis is appropriate for a crossover study with repeated measurements.

The dependent variables were changes from baseline in the NRS in the cold-pressor pain model. For all analyses, pairwise comparisons between the treatments will be made only if the overall test for the difference between all treatments was significant at the level of 0.05. This Fisher's least significant difference method provides protection for multiple comparisons. Data will be analyzed in SPSS.

The primary endpoint is NRS during CPR at time zero

The secondary endpoint is NRS during CPR at time 15 min

Statistical hypothesis test:

- Null hypothesis: The difference in pain between the treatment (metoxyflurane) is at least 0.5 point on the 0-10 NRS scale in favor of the control treatment (fentanyl 0.05 mg).
- Alternative hypothesis: The difference in pain between the treatment (metoxyflurane) is less than 0.5 point on the 0-10 NRS scale in favor of the control treatment (fentanyl 0.025 mg).

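### The only aim is to find equipotent doses, but the plan neither defines equipotence nor estimates the fentanyl dose that matches 3 ml methoxyflurane

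*Combined protocol and SAP*

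**What the plan says.** Section 2 states the aim: "The aim of this study is to determinate equipotent doses of inhaled metoxyflurane vs. intravenous fentanyl". The synopsis and sections 1.1 and 1.3 repeat it, and no other aim is given.

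The design has four conditions per volunteer: placebo, fentanyl 0.025 mg (F1), fentanyl 0.05 mg (F2) and methoxyflurane 3 ml (M). Section 1.3 explains the choice: "From these data we have chosen two doses of fentanyl to be compared with 3 ml Pentrox: 0.025 mg and 0.05 mg intravenous". It also plans comparisons with placebo. The doses are fixed (section 5.5: "No dose modifications are allowed").

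Section 10.5.1 plans a linear mixed model that compares treatments on change from baseline in NRS, and adds that "pairwise comparisons between the treatments will be made only if the overall test for the difference between all treatments was significant". It then states a hypothesis pair with a one-sided margin of 0.5 NRS. The null names fentanyl 0.05 mg and the alternative names 0.025 mg.

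Two other passages bear on the point. Section 6.1 describes three pilots and a protocol change "If the pilots demonstrate large differences in the CPT scores at time zero between the selected fentanyl doses and metoxyflurane"; it does not say what counts as large. Section 10.4 defers further analysis detail to a separate SAP, to be signed before database lock. No such SAP is in the supplied text.

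**The concern.** The answer to the stated aim is a dose: the amount of fentanyl that gives the same mean NRS change as 3 ml methoxyflurane. The planned outputs are NRS differences between treatments. Turning those into a dose needs a rule for calling two doses equipotent, or an estimate on the fentanyl scale, and the supplied text has neither.

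Without one, the trial can run exactly as planned and leave the reader to decide what a set of pairwise results means for potency. Two fentanyl doses that differ twofold might both look compatible with 3 ml, or neither might. Repairing the mismatched doses in the hypothesis pair would not cure this, because a one-sided margin shows only that methoxyflurane is not much worse than a given fentanyl dose.

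**Working it through.** **1. The plan's own figure.** Section 10.1 says "A sample size of 10 will have 80% power to detect a difference in means of 0,500", with an SD of differences of 0.5, "using a paired t-test with a 0,050 two-sided significance level". The noncentrality is √n × 0.5/0.5 = √n. Exact power from the noncentral t is 74.8% at n = 9, 80.3% at n = 10 and 88.3% at n = 12. The stated 10 reproduces. It is a sample size for detecting a difference between two conditions, not for estimating a dose.

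**2. What pairwise equivalence would give.** From the plan: n = 12, SD of differences 0.5, margin 0.5, overall test at 0.05. Assumed here: a two-sided equivalence test (two one-sided tests at 0.05) after the overall test, a linear dose response through placebo, and 3 ml truly midway at 0.0375 mg.

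- SE of a treatment difference = 0.5/√12 = 0.144. With 3 × 11 = 33 residual df, the 90% half-width is 1.692 × 0.144 = 0.244.
- A dose passes if the observed difference is below 0.5 − 0.244 = 0.256 in absolute value.
- The true M–F1 and M–F2 differences are half the step: 0.125, 0.25 or 0.5 for steps of 0.25, 0.5 or 1.0 NRS per 0.025 mg.

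Simulation (20,000 trials per scenario):

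| NRS per 0.025 mg | Result with 3 ml midway |
|---|---|
| 0.25 | both pass in about 50% |
| 0.5 | both 20%, neither 16%, one only about 64% |
| 1.0 | neither in 90% |

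If 3 ml equals F1 or F2 and the step is at least 0.5, that dose alone is named in about 88-92% of trials.

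**3. The plan's one-sided margin, applied to each dose.** This run used one-sided 0.025 and assumed that 0.025 mg lowers NRS by 1.0 against placebo. If 3 ml equals 0.05 mg, both doses pass in about 92% of trials. If 3 ml is 1 NRS better than 0.05 mg (F1–F2 gap 0.5), both pass in about 100%. This reading cannot separate equal from stronger.

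**4. What the same data give as a dose.** Write NRS change as a reduction, with C, F1, F2 and M the arm means.

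- Slope per step: b = (F2 − C)/2.
- Offset: y = M − (C + F1 + F2)/3.
- Matching dose = 0.025 × (1 + y/b) mg.
- Residual variance is 0.5²/2 = 0.125, so Var(b) = 0.125/(2 × 12) = 0.00521 and Var(y) = (4/3) × 0.125/12 = 0.01389, with zero covariance.

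Fieller limits at the expected values for a step of 0.5 (b = 0.5, y = 0.25, t² = 2.035² = 4.14):

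- A = 0.25 − 4.14 × 0.00521 = 0.228
- B = 0.5 × 0.25 = 0.125
- C′ = 0.0625 − 4.14 × 0.01389 = 0.005
- y/b limits = (B ± √(B² − A·C′))/A = (0.125 ± 0.120)/0.228, or about 0.02 and 1.07
- Dose limits: about 0.026 and 0.052 mg

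The simulated median interval agrees: 0.026-0.052 mg at a step of 0.5, and 0.032-0.044 mg at 1.0. At 0.25 it is about 0.013-0.072 mg when finite, and it is not finite in about 8% of trials.

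**5. How far linearity can be checked.** Three fentanyl levels leave one degree of freedom for lack of fit. With true reductions of 1.0 (F1) and 1.5 (F2), the check rejects linearity in only about 49% of trials. If 3 ml then equals F1, the straight-line estimate has median 0.0305 mg instead of 0.025 mg.

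**The case against.** - **No such decision rule.** A reader might infer that the plan will declare both doses, or neither, equipotent. The documents do not support that. Section 10.5.1 has no two-sided equivalence test, so those rates show what one plausible reading would produce.
- **The midpoint is an assumption.** It is tempting to say that the two doses were chosen to surround 3 ml. Section 1.3 takes them from retrospective intranasal data, and section 6.1 asks only whether they are representative. If 3 ml equals a tested dose and the step is at least 0.5 NRS, pairwise equivalence does well. That stands, but nothing in the documents establishes such a match.
- **Partial safeguards.** The pilots could prompt a protocol change, the promised SAP could add an estimate, and arm means will be available for interpolation afterwards. All true. But the pilots estimate no dose, nothing supplied commits the SAP to one, and interpolation chosen after unblinding is not prespecified.
- **A dose estimate is not always sharp.** This stands. In a rerun at 0.25 NRS per step, the interval covered both tested doses or was unbounded in 69% of trials. An out-of-range rule based on the point estimate would also misfire: if 3 ml equals 0.05 mg, about 50% of estimates fall above it.

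**Conclusion.** The concern holds as a mismatch between aim and analysis: one aim, a dose, and no criterion or estimate in the supplied text that yields one. The sample-size arithmetic is correct.

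The size of the problem depends on the unknown fentanyl step and on where 3 ml falls. The rates in steps 2 and 3 rest on rules and dose-response assumptions that are not in the documents, and should be read as conditional. They do not show that the trial must fail to answer its aim. Nor can the data always place 3 ml on the fentanyl scale: the interval is useful at about 0.5 NRS per step or more, and wide at about 0.25.

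**What to change.** In section 10.5.1, or in the SAP before database lock:

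1. Prespecify the fentanyl-equivalent dose of 3 ml at time zero as the estimate that answers the aim. Derive it from the planned mixed model using control, F1 and F2, with a 95% Fieller or bootstrap interval. Repeat it for the 15-minute CPT.
2. Report the estimate and interval in every case. State 'outside the studied range' only when the whole interval lies beyond 0-0.05 mg. If the interval is unbounded, say that the dose cannot be determined.
3. Add a sensitivity analysis that does not assume a straight line through zero, such as piecewise or log-dose interpolation between F1 and F2.
4. Keep the pairwise comparisons, including those with placebo, and reconcile the two fentanyl doses named in the null and the alternative.

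The cost is wording and one derived estimate, with no new volunteers, visits or treatment conditions. The downsides are the dose-response shape assumption and possibly a wide or unbounded interval if the two fentanyl doses differ little in effect.

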2 STUDY OBJECTIVES AND RELATED ENDPOINTS

The aim of this study is to determinate equipotent doses of inhaled metoxyflurane vs. intravenous fentanyl. We have chosen to compare with fentanyl because it is a well-known drug in clinical practice. In addition, both drugs have a fast onset (minutes) and the analgesic effect last for approximately the same time interval (20-30 min). Therefore, they are comparable in a clinical setting.

- 2.1 **Primary Endpoint** NRS (numeric rating scale) scores during CPT 5 minutes after drug administration.
- 2.2 **Secondary Endpoints** NRS scores during CPT 20 minutes after drug administration (15 min after last CPT).

The table below represent the study's timeline:

Time (min)	- 15	-10	-5	0	5	10	15
Control (C)	CPT		placebo (NaCl) i.v. placebo (NaCl) inhal; continuous	CPT			CPT
Fentanyl (F1)	CPT		F1 0.025 mg i.v. placebo (NaCl) inhal; continuous	CPT			CPT
Fentanyl (F2)	CPT		F2 0.05 mg i.v. placebo (NaCl) inhal; continuous	CPT			CPT
Metoxyflurane (M)	CPT		placebo (NaCl) i.v. M 3 ml inhal; continuous	CPT			CPT

3 OVERALL STUDY DESIGN

The study is a phase 4

This is a randomized, double blind, placebo-controlled crossover study in volunteers

Study Period	Estimated date of first patient enrolled: 01.03.2019 Anticipated recruitment period: 22 months Estimated date of last patient completed:31.12.2020
Treatment Duration:	2 h x 4. Totally 8 hours
Follow-up:	No further follow-up after the four sessions.

